10.1. Anticipated Adverse Effects

As per the commercial DFU included with the study devices, the potential complications associated with the use of the Expect Needle may include, but are not limited to:

- Bleeding
- Perforation
- Pancreatitis
- Infection
- Peritonitis
- Inflammation
- Aspiration
- Fever
- Allergic Reaction to Medication
- Hypotension
- Respiratory Depression or Arrest
- Cardiac Arrhythmia or Arrest
- Tumor Seeding

10.2. Definitions and Classification of Adverse Events

Adverse event definitions provided below are extracted from References ISO 14155-2011 and MEDDEV 2.7/3 12/2010 as indicated.

Figure 6 - Adverse Event Definitions

Term	Definition
Adverse Event (AE) Ref: ISO 14155-2011	
Any untoward medical occurrence, unintended disease or injury, or untoward clinical signs (including abnormal lab findings) in subjects, users or other persons, whether or not related to the investigational medical device. This includes events related to:
 
 • The investigational medical device or comparator • The procedures involved (study-required) 
For users/other persons, this definition is restricted to events related to the investigational device
 
Note: In this study, reported AEs will include unanticipated events such as unplanned hospital admission or overnight observation, laboratory or radiological investigation which confirms pancreatitis,

Figure 6 - Adverse Event Definitions

Term	Definition
	bleeding, or perforation, or any other event deemed by the Investigator to be unanticipated and attributable to the EUS-FNA procedure.
Adverse Device Effect (ADE) Ref: ISO 14155-2011	
Adverse event related to the use of an investigational medical device:
 
 • This includes adverse events resulting from insufficient or inadequate instructions for the use, deployment, implantation, installation or operation, or any malfunction of the investigational medical device. • This includes any event resulting from use error or from intentional misuse of the investigational medical device.
Serious Adverse Event (SAE) Ref: ISO 14155-2011	
An adverse event that:
 
 • Led to death • Led to a serious deterioration in the health of the subject that either resulted in: 
 ○ a life-threatening illness or injury, or ○ a permanent impairment of a body structure or a body function, or ○ in-patient hospitalization or prolonged hospitalization (of an existing hospitalization), or ○ medical or surgical intervention to prevent life-threatening illness or injury or permanent impairment to a body structure or a body function • Led to fetal distress, fetal death, or a congenital abnormality or birth defect. 
Note: Planned hospitalization for a pre-existing condition, or a procedure required by the protocol, without serious deterioration in health, is not considered a serious adverse event.

Serious Adverse Device Effect (SADE) Ref: ISO 14155-2011	
An adverse device effect that has resulted in any of the consequences characteristic of a serious adverse event.
 
Note: All SAEs that could have led to a SADE if suitable action had not been taken or if circumstances had been less fortunate shall be reported as required by the local IRB/EC, national regulations, or the protocol. If applicable, see MEDDEV 2.7/3 12/2010 for reporting timeline requirements.

Unanticipated Serious Adverse Device Effect (USADE)	
A serious adverse device effect which by its nature, incidence, severity, or outcome has not been identified in the current version of the risk analysis report.
 
Note: An anticipated serious adverse device effect (ASADE) is an

Figure 6 - Adverse Event Definitions

Term	Definition
Ref: ISO 14155-2011	effect which by its nature, incidence, severity or outcome has been identified in the risk analysis report.
Device Deficiency Ref: ISO 14155-2011 Ref: MEDDEV 2.7/3 12/2010	
A device deficiency is any inadequacy of a medical device with respect to its identity, quality, durability, reliability, safety or performance.
 
Note: Device deficiencies include malfunctions, use errors, and inadequate labeling.
 
Note: All device deficiencies that could have led to a SADE if suitable action had not been taken or if circumstances had been less fortunate shall be reported as required by the local IRB/EC, national regulations, or the protocol. If applicable, see MEDDEV 2.7/3 12/2010 for reporting timeline requirements.

Abbreviations: EC=Ethics Committee; IRB=Institutional Review Board

Underlying diseases are not reported as AEs unless there is an increase in severity or frequency during the course of the investigation. Death should not be recorded as an AE, but should only be reflected as an outcome of a specific SAE.

Reporting requirements are provided in **Section 10.4** below.

Refer to **Section 10.1** above for the known risks associated with the study device(s) and EUS-FNA procedure.

10.3. Relationship to Study Device(s)

The Investigator must assess the relationship of the AE to the study devices as related or unrelated using criteria outlined below.

- AE Unrelated to Study Device:
 - The adverse event is determined to be due to a concurrent illness or effect of another device/drug and is not related to the investigational product.
- AE Related to Study Device:
 - The adverse event is determined to be potentially related to the investigational product, and an alternative etiology is equally or less likely compared to the potential relationship to investigational product.
 - There is a strong relationship to investigational product, or recurs on re-challenge, and another etiology is unlikely.
 - There is no other reasonable medical explanation for the event.

Unrelated AEs will not be documented.

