4.2. Secondary Endpoints

Safety Endpoint

- Occurrence, severity and relatedness of adverse events to the needle and procedure.

Other Endpoints

- b. Extent of cyst aspiration as measured by reduction of maximal cyst diameter before and after FNA (converted to volume by standard geometric formulation).
- c. Successful echoendoscopic fine needle aspiration of PCL, defined as complete cyst aspiration or collection of aspirate adequate to perform two standard assays: cytology and carcinoembryonic antigen (CEA).

NOTES: Endpoint c) success is defined as:

- complete aspiration, defined as reaching a final cyst maximal diameter of less than 5mm attained with a maximum of 3 needle passes; in the case of a multilocular cyst, complete aspiration of the largest locule is required,

or

- collection of aspirate adequate to perform two standard assays: cytology and CEA, attained with a maximum of 3 needle passes

Total aspirate volume should be 3cc or more. In cases where less than 3cc of aspirate is obtained but cytology and CEA assays can be adequately completed, the primary endpoint is considered to have been met. Aspirate handling procedures are provided in Section 7.4 below.

- d. Ability to reach and penetrate the PCL, stratified by route of access and PCL location.
- e. Number of EUS-FNA needles and EUS-FNA needle passes* used.
- f. Time needed for aspiration for each pass and time from first needle pass in[†] to last needle pass out[‡].

DEFINITIONS:

**Needle pass* -- from needle insertion through needle removal outside the cyst lumen, but not including needle repositioning within a single or multi-compartment cyst.

Note: A maximum of 3 needle passes are allowed, after which the EUS-FNA procedure will be considered failed.

[†]*Time of first needle pass in* -- time of the first needle puncture into the cyst lumen.

[‡]*Time of last needle pass out* -- time of removal of needle outside the cyst lumen at the end of the last fluid aspiration from a single or multi-loculated cyst, or after 10 seconds of failed attempt to aspirate fluid after the last needle re-positioning in a single or multi-compartment cyst.

- g. Ease of needle passage in and out of echoendoscope and quality of needle visualization inside the cyst, categorized as *Excellent, Very Good, Good, Fair, and Poor*.

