8.6. Long Term Clinical Follow-Up Chart Review

After completion of the 30-day Follow-up Visit, a retrospective Long Term Clinical Follow-Up Chart Review will be performed to collect up to 24 months of standard of care clinical information (if applicable). There are no office or telephone visits required. The Investigator or study coordinator will review the hospital charts to assess patient status and extract PCL characteristic pertaining to Morphological Status, Cytopathological Status, Biochemical Status, and Surgical Pathology. No new Adverse Event information will be captured after the 30 Day Post Procedure.

9. Statistical Considerations

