10.4. Reporting Requirements to Sponsor

10.4.1. *Communication Method*

Reporting of adverse events and device deficiencies or malfunctions as outlined by category and as applicable during the entire duration of the study, from signing of the ICF through completion of an end-of-study report, should be made by entering pertinent information into the associated study data base fields. In case access to the electronic case report forms is not possible, the Investigator or site study staff members should contact the Sponsor Global Safety Office and Sponsor Project Manager by e-mail. If e-mail communications are also impossible, then one of these Boston representatives should be contacted by telephone. Contact information for the Sponsor Global Safety Office and Sponsor Project Manager will be provided and kept up to date by Sponsor at all times.

Upon receipt of these communications, associated source documentation may be requested by the Sponsor Global Safety Office and Sponsor Project Manager.

10.4.2. *Communication Timelines*

The following should be reported to Sponsor within 2 business days:

- All Serious Adverse Events (SAEs), whether related to the EUS-FNA devices and/or procedure or not
- Device Deficiencies, Failures, Malfunctions, and Product Nonconformities that led to any Adverse Event (AE) or Serious Adverse Event (SAE).

The following should be reported to Sponsor **within 10 business days**:

- All non-serious Adverse Events (AEs) related to the EUS-FNA devices and/or procedure
- Device Deficiencies, Failures, Malfunctions, and Product Nonconformities that did not lead to an Adverse Event (AE) or Serious Adverse Event (SAE).

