- Create and maintain source documents throughout the clinical study and ensure their availability with direct access during monitoring visits or audits; ensure that all clinical-investigation-related records are retained per requirements.
- Ensure the accuracy, completeness, legibility, and timeliness of the data reported to the Sponsor in the CRFs and in all required reports.
- Record, report, and assess (seriousness and relationship to the device/procedure) every adverse event and observed device deficiency.
- Report to the Sponsor, per the protocol requirements, all SAEs and device deficiencies that could have led to a SADE.
- Report to the EC/IRB any SAEs and device deficiencies that could have led to a SADE, if required by the national regulations or this protocol or by the EC/IRB, and supply the Sponsor with any additional requested information related to the safety reporting of a particular event.
- Maintain the device accountability records as needed.
- Allow the Sponsor to perform monitoring and auditing activities, and be accessible to the monitor and respond to questions during monitoring visits.
- Ensure that informed consent is obtained in accordance with this protocol and local EC/IRB requirements.
- Provide adequate medical care to a subject during and after a subject's participation in a clinical study in the case of adverse events, as described in the ICF.
- Inform the subject of the nature and possible cause of any adverse events experienced.
- Inform the subject of any new significant findings occurring during the clinical investigation, including the need for additional medical care that may be required.

- Ensure that clinical medical records are clearly marked to indicate that the subject is enrolled in this clinical study.
- Inform, with the subject's approval or when required by national regulations, the subject's personal physician about the subject's participation in the clinical investigation.
- Make all reasonable efforts to ascertain the reason(s) for a subject's premature withdrawal from clinical investigation while fully respecting the subject's rights.

Ensure that an adequate investigation site team and facilities exist and are maintained and documented during the clinical investigation.

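### Protocol 10.3 tells sites not to document unrelated AEs, which conflicts with the other AE sections, and its device-only relatedness scale cannot supply the procedure-relatedness that safety endpoint a needs

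*Protocol*

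**What the plan says.** Protocol 10.3 sets up one two-level scale: "The Investigator must assess the relationship of the AE to the study devices as related or unrelated using criteria outlined below". An event counts as unrelated when it is put down to a concurrent illness or to another device or drug. The section closes with "Unrelated AEs will not be documented", with no exception for serious events or for events caused by the procedure.

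Other parts of the plan set a wider scope:

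- Section 10.4.2 requires within 2 business days "All Serious Adverse Events (SAEs), whether related to the EUS-FNA devices and/or procedure or not". Within 10 business days it requires non-serious events related to the devices, the procedure, or both.
- Appendix B.10 makes the investigator responsible to "Record, report, and assess (seriousness and relationship to the device/procedure) every adverse event and observed device deficiency".
- Section 9.3 and SAP 4.1 say that adverse events arising in or from a treatment attempt are collected.
- Section 10.8 has the sponsor review listings of device- or procedure-related events and of all SAEs.
- Safety endpoint a in section 4.2, repeated in SAP 5.1.1, is "Occurrence, severity and relatedness of adverse events to the needle and procedure".

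On timing, section 10.4.1 describes reporting "from signing of the ICF through completion of an end-of-study report", as applicable by category. Section 8.6 says "No new Adverse Event information will be captured after the 30 Day Post Procedure".

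**The concern.** Under 10.3, relatedness is not just an attribute of a recorded event. It decides whether the event is recorded at all. The filter acts at data entry, and little downstream would pick up an omission: Appendix B.12 plans no regular on-site monitoring, database queries cannot find an event that was never entered, and the chart review in 8.6 collects no new adverse events.

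The scale is also narrower than the endpoint. An event caused by the EUS-FNA procedure but not by the needle has no category of its own in 10.3. On the only scale given, it is unrelated to the study device. At stake are the completeness of the one designated safety endpoint, the listings and threshold comparisons in 10.8, and consistency of collection across 7 to 12 centers.

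**Working it through.** No arithmetic applies. The check is to take each type of event and ask what each section tells a site to do with it.

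1. **SAE unrelated to device and procedure.** 10.3: do not document. 10.4.2: report within 2 business days. B.10: record, report and assess. 10.8: include in the SAE listing. Direct contradiction.
2. **Non-serious event related to the procedure but not the needle.** 10.3: unrelated on the device scale, so do not document. 10.4.2: report within 10 business days. B.10: record, with relationship to device/procedure. 10.8: include in the listing. Endpoint a: needed. Direct contradiction, and the type most exposed to loss.
3. **Non-serious event unrelated to both.** 10.3: do not document. 10.4.2: not requested. B.10: record. Contradiction with B.10, and with 9.3 and SAP 4.1 if the event arises during the treatment attempt.
4. **Event related to the device.** All sections agree that it is captured.

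The second type is not hypothetical. Section 7.1 gives every patient antibiotics, and section 10.1 lists allergic reaction to medication, hypotension and respiratory depression among the potential complications. A drug reaction of that kind can meet the 10.3 definition of unrelated, because that definition includes the effect of another drug.

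**Relatedness criteria.** 10.3 gives criteria for the device. B.10 and 10.4.2 mention the procedure but give none. The SAP repeats the endpoint wording without deriving relatedness; its adverse-event rules in 7.4 cover missing and partial onset dates. Neither document therefore says how procedure-relatedness is to be judged.

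**Reporting period.** Sections 7.5 and 8.5 collect events from the procedure to the 30-day contact (window 25 to 35 days), and 8.6 collects no new events after that. Section 7.5 also censors events at surgery or another major intervention before day 30. Section 10.4.1 starts at consent and ends at the end-of-study report. The time between consent and procedure, and the time after day 30, fall under 10.4.1 only. Because 10.4.1 says that it operates as applicable by category and also covers device deficiencies, this is a looser mismatch than those above.

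**The case against.** The strongest reply is that one sentence in 10.3 is outweighed by the rest of the protocol. Section 10.2 names 10.4 as the place for reporting requirements, and 10.4.1 has those events entered in the study database. Section 7.5 puts immediate and delayed complications on the AE CRF with no relatedness filter. The Figure 6 note names unplanned admission, confirmed pancreatitis, bleeding and perforation, and other unanticipated events attributable to the EUS-FNA procedure, as reported events. The 10.8 listings have the scope of 10.4.2, not of 10.3. The AE CRF is not in the documents, so it may already hold a procedure-relatedness field. Limited collection can also be a legitimate choice for marketed needles.

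Most of this stands, and it is why loss is only possible. It does not remove the contradiction. Reading 10.3 as meaning only non-serious events unrelated to both device and procedure is sensible, but the text does not say so, and that reading would still conflict with B.10.

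A reader might go further and infer that the safety comparison between arms is biased, because the operator who judges relatedness knows which needle was used. The documents do not support that step. They give no adverse-event rate and no fraction of events that would be discarded, and no reason why that fraction should differ by arm. Causes such as sedation or the echoendoscope are common to all three arms. Section 10.3 also counts an event as related when the alternative cause is only equally likely. SAP 5.1.1 plans descriptive summaries, so no between-arm safety test is planned that could be distorted.

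Nor do the documents support inferring that every event judged unrelated to the needle is lost for good, or that the 10.8 thresholds will necessarily be compared with filtered counts. Either would require 10.3 to override every other section.

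**Conclusion.** The point holds as an internal inconsistency with a practical consequence. Two kinds of event that the plan elsewhere requires, unrelated SAEs and procedure-related non-needle events, are excluded by 10.3 read literally. A third, non-serious events unrelated to both, is excluded by 10.3 and required by B.10. The written criteria cannot supply half of what safety endpoint a asks for.

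The consequence is possible under-capture that may vary by site, according to which section a site follows. Its size cannot be derived from the documents, and neither can a direction of bias between arms. The conclusion rests on reading 10.3 as written and makes no assumption about the content of the AE CRF. The primary endpoint and endpoint c are untouched. The change should be made, because an event omitted at entry is hard to restore later.

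**What to change.** - **Section 10.3:** delete the closing sentence. At minimum, limit it to non-serious events unrelated to both device and procedure, and align B.10 with that narrower scope. Check 9.3 and SAP 4.1 against whichever scope is chosen.
- **Relatedness:** require two separate assessments, needle and procedure, each with written criteria. Add the procedure item to the AE CRF if it is not already there.
- **SAP 5.1.1:** tabulate endpoint a by relatedness to needle and by relatedness to procedure.
- **Reporting period:** reconcile 10.4.1 with 7.5, 8.5 and 8.6. State whether collection starts at consent or at the procedure, and keep the censoring rule in 7.5.

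The cost is protocol and SAP wording, possibly one CRF item, and possibly some additional non-serious events to enter. The narrower option keeps that last cost down.

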10.4. Reporting Requirements to Sponsor

10.4.1. *Communication Method*

Reporting of adverse events and device deficiencies or malfunctions as outlined by category and as applicable during the entire duration of the study, from signing of the ICF through completion of an end-of-study report, should be made by entering pertinent information into the associated study data base fields. In case access to the electronic case report forms is not possible, the Investigator or site study staff members should contact the Sponsor Global Safety Office and Sponsor Project Manager by e-mail. If e-mail communications are also impossible, then one of these Boston representatives should be contacted by telephone. Contact information for the Sponsor Global Safety Office and Sponsor Project Manager will be provided and kept up to date by Sponsor at all times.

Upon receipt of these communications, associated source documentation may be requested by the Sponsor Global Safety Office and Sponsor Project Manager.

10.4.2. *Communication Timelines*

The following should be reported to Sponsor within 2 business days:

- All Serious Adverse Events (SAEs), whether related to the EUS-FNA devices and/or procedure or not
- Device Deficiencies, Failures, Malfunctions, and Product Nonconformities that led to any Adverse Event (AE) or Serious Adverse Event (SAE).

The following should be reported to Sponsor **within 10 business days**:

- All non-serious Adverse Events (AEs) related to the EUS-FNA devices and/or procedure
- Device Deficiencies, Failures, Malfunctions, and Product Nonconformities that did not lead to an Adverse Event (AE) or Serious Adverse Event (SAE).

10.5. Reporting Requirements to EC/IRB

The Principal Investigator is responsible for informing the EC/IRB of AEs and SAEs as required by local procedure. These reporting requirements may vary from one EC/IRB to another.

The Sponsor is responsible for reporting AE and SAE information to participating Investigators as required by local procedures at individual Investigational sites.

10.6. Return of Devices to Sponsor

All device deficiencies (including but not limited to failures, malfunctions, product nonconformities, and labeling errors) will be documented and reported to the Sponsor as

detailed in **Section 10.4** above. If possible, the device(s) related to an observed device deficiency should be returned to the Sponsor for analysis. Instructions for returning the investigational device(s) are provided in **Appendix B.9**.

10.7. Potential Risks and Benefits Associated with Study Participation

Patients enrolled in this study were scheduled to undergo a EUS-FNA procedure for assessment of a PCL. The EUS-FNA procedures in this study are performed per DFU and standard of practice. The EUS-FNA needles are commercially available devices. Thus, there is no known added risk resulting from undergoing the EUS-FNA procedure in this study compared to outside of this study.

Patients randomized to the standard 19 G or 22 G EUS-FNA needles and in whom the PCL could not be accessed or complete cyst aspiration cannot be attained, will receive a second attempt at adequate PCL aspiration using the marketed, novel 19 G Flex EUS-FNA needle design. Thus, in a subset of patients, there is an added potential benefit to undergoing the EUS-FNA procedure in this study compared to outside of this study.

